13.7.1.6. Monitoring and Follow-up of Adverse Events

Subjects having AEs will be monitored with relevant clinical assessments and laboratory tests, as determined by the investigator. All follow-up results are to be reported to the sponsor personnel or the authorized medical monitor. Any actions taken and follow up results must be recorded either on the appropriate page of the eCRF or in appropriate follow-up written correspondence, as well as in the subject's source documentation. Follow-up laboratory results should be filed with the subject's source documentation.

For all AEs that require the subject to be discontinued from the study, relevant clinical assessments and laboratory tests must be repeated at appropriate intervals until final resolution, stabilization of the event(s), or until the subject is lost to follow-up or dies.

Subjects with AEs that are ongoing at study completion or study withdrawal must be followed until resolution or for 30 days after the last study visit, whichever comes first.

13.7.1.7. Treatment-Emergent Adverse Events

Treatment-emergent AEs are defined as AEs that begin or worsen after the first dose of IMP.

13.7.2. Serious Adverse Events

13.7.2.1. Definition of Serious Adverse Event

An SAE is defined as any AE occurring at any dose that results in any of the following outcomes:

- results in death;
- is life threatening;
- requires inpatient hospitalization or prolongation of existing hospitalization;
- results in persistent or significant disability/incapacity, or substantial disruption of the ability to conduct normal life functions;
- is a congenital anomaly/birth defect; or
- is an important medical event.

Note: Hospitalization is defined as a formal inpatient admission. This will not include admissions under "23-hour Observational Status," an emergency room visit without hospital admission, or an urgent care visit and therefore such events will not be recorded as an SAE under this criterion, nor will hospitalization for an elective or outpatient procedure scheduled or planned before signing of informed consent. However, unexpected complications and/or prolongation of hospitalization that occur during elective or outpatient surgery should be recorded as AEs and assessed for seriousness. Admission to the hospital for social or situational

reasons (eg, no place to stay live too far away to come for hospital visits) will not be considered inpatient hospitalizations.

Important medical events that may not result in death, be life threatening, or require hospitalization may be considered an SAE when, based upon appropriate medical judgment, they may jeopardize the subject and may require medical or surgical intervention to prevent one of the outcomes listed in this definition. Examples of such medical events include allergic bronchospasm requiring intensive treatment in an emergency room, blood dyscrasias, convulsions that do not result in inpatient hospitalization, or the development of drug dependency or drug abuse.

Any clinical endpoints that meet SAE criteria will be also reported as SAEs.

13.7.2.2. Definition of Adverse Events or Outcomes Not Qualifying as Serious Adverse Events

The following are not considered SAEs and therefore do not need to be reported as such:

- Preplanned or elective hospitalization, including social and/or convenience situations (eg, due to inclement weather).
- Overdose of either Esperion IMP or concomitant medication unless the event meets SAE criteria (eg, hospitalization). However, the event should still be captured as a nonserious AE on the appropriate eCRF page.

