13.7.1.3. Reporting of Adverse Events

All AEs that occur from the time the ICF is signed through 30 days after the last study visit should be recorded on the eCRF. Any SAE that occurs from the time the ICF is signed through 30 days after the last study visit should be reported to the sponsor per [Section 13.7.2.4](#).

Subjects should be instructed to report any AE that they experience from the time the ICF is signed through 30 days after the last dose of IMP to the investigator. Investigators should make an assessment for AEs at each visit and record the event on the appropriate eCRF.

Wherever possible, a specific disease or syndrome rather than individual associated signs and symptoms should be identified by the investigator and recorded on the eCRF. However, if an observed or reported sign or symptom is not considered a component of a specific disease or syndrome by the investigator, it should be recorded as a separate AE on the eCRF. Additionally, the condition that led to a medical or surgical procedure (eg, surgery, endoscopy, tooth extraction, transfusion) should be recorded as an AE, not the procedure.

Any medical condition already present at screening or baseline should not be reported as an AE unless the medical condition or signs or symptoms present at baseline change in severity or seriousness at any time during the study. In this case, it should be reported as an AE.

Clinically significant abnormal laboratory or other examination (eg, ECG) findings that are detected during the study or are present at baseline and significantly worsen during the study should be reported as AEs. The investigator will exercise his or her medical and scientific judgment in deciding whether an abnormal laboratory finding or other abnormal assessment is clinically significant. Significant abnormal laboratory values occurring during the clinical study will be followed until repeat tests return to normal, stabilize, or are no longer clinically significant. Any abnormal test that is determined to be an error does not require reporting as an AE.

Each AE is to be evaluated for duration, severity, seriousness, and causal relationship to the investigational drug. For each AE, the following information will be recorded:

- description of the event (eg, headache);
- date of onset;
- date of resolution (or that the event is continuing);
- action taken because of the event;
- seriousness of the event;
- severity of the event;
- outcome of the event; and

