13.7.2.4. Reporting Serious Adverse Events

All SAEs, regardless of relationship to IMP, occurring from the time of informed consent until 30 days following the last dose of IMP (for most subjects 30 days after Visit T3, must be reported by the principal investigator or designee to the authorized safety designee within 24 hours of the principal investigator or the clinical site becoming aware of the occurrence. All SAEs that the investigator considers related to IMP that occur after the 30-day follow-up of the study period must be reported to the sponsor.

To report the SAE, complete the provided SAE form and submit it to the safety designee within 24 hours of becoming aware of the occurrence.

The investigator is required to submit SAE reports to the IRB in accordance with local requirements. All investigators involved in studies using the same investigational product will

receive any safety alert notifications for onward submission to their local IRB as required. All reports sent to investigators will be blinded.

All SAEs should be recorded on the eCRF and source documents. Criteria for documenting the relationship to IMP and severity will be the same as those previously described.

The investigator must continue to follow the subject until the SAE has subsided or until the condition becomes chronic in nature, stabilizes (in the case of persistent impairment), or the subject dies.

Within 24 hours of receipt of follow-up information, the investigator must update the SAE form and submit any supporting documentation (eg, subject discharge summary or autopsy reports) to the safety designee.

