13.7.2.5. Reporting of Serious Adverse Events to Regulatory Authorities

The sponsor (and/or designee) is responsible for submitting expedited reports of suspected and unexpected serious adverse reactions (SUSARS) to the appropriate regulatory authorities. All investigators participating in ongoing clinical studies with the IMP will be notified by the sponsor (or designee) of SUSARs. SUSARS must be communicated as soon as possible to the appropriate IRB by the investigator, as applicable and/or reported in accordance with local laws and regulations. Investigators should provide written documentation of IRB notification for each report to the sponsor.

Serious AEs that are anticipated to occur in this subject population will be collected and reported by the investigator as described in [Section 13.7.2.4](#). However, these events will not be submitted to the regulatory authorities as expedited reports unless they meet SUSAR criteria. The events that are considered exempt from expedited reporting include the following clinical endpoints:

- cardiovascular death;
- nonfatal myocardial infarction;
- nonfatal stroke;
- unstable angina requiring hospitalization;
- coronary revascularization;
- heart failure requiring hospitalization; and
- noncoronary arterial revascularization.

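### Protocol 13.7.2.2 exempts all elective hospitalization from SAE status, while 13.7.2.1 exempts it only if planned before consent, so one narrow class of admission has two answers

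*Protocol*

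**What the plan says.** Protocol 13.7.2.1 defines an SAE by its outcome. One of the listed outcomes is that the event "requires inpatient hospitalization or prolongation of existing hospitalization". A note then narrows what counts as hospitalization. It leaves out observation stays, emergency and urgent-care visits without admission, and social or situational admissions. For elective care the exclusion depends on timing: "nor will hospitalization for an elective or outpatient procedure scheduled or planned before signing of informed consent". The note adds a safeguard: "However, unexpected complications and/or prolongation of hospitalization that occur during elective or outpatient surgery should be recorded as AEs and assessed for seriousness".

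Protocol 13.7.2.2 is a separate list, introduced by "The following are not considered SAEs and therefore do not need to be reported as such". Its first bullet is "Preplanned or elective hospitalization, including social and/or convenience situations (eg, due to inclement weather". Its second bullet, on overdose, exempts the event unless it meets SAE criteria.

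Three other places use the classification:

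- Protocol 13.7.1.3 says that "the condition that led to a medical or surgical procedure (eg, surgery, endoscopy, tooth extraction, transfusion) should be recorded as an AE".
- Protocol 13.7.2.4 requires a report within 24 hours for "All SAEs, regardless of relationship to IMP, occurring from the time of informed consent until 30 days following the last dose of IMP".
- SAP 5.5.1 tabulates treatment-emergent SAEs by treatment group. It gives no SAE definition of its own.

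**The concern.** An investigator whose subject is admitted electively during the trial may turn to either section. In 13.7.2.1 the question is when the procedure was planned. In 13.7.2.2 the words preplanned and elective are joined by "or" without any time limit, so being elective is enough by itself. For an admission arranged after consent, the two sections give opposite answers.

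SAEs are a named safety endpoint in protocol 6.4.4 and SAP 3.4. SAE status also triggers the 24-hour report, submission to the IRB under local requirements, and follow-up until the event subsides, stabilizes or becomes chronic (13.7.2.4). If sites apply different sections, the SAE count depends partly on which page was read. An event that should have been reported promptly may instead appear only as a non-serious AE.

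**Working it through.** The point rests on wording. The plan has no figure to reproduce, so the check sets the two sections side by side for each kind of admission.

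| Inpatient admission | 13.7.2.1 | 13.7.2.2, read literally | Conflict? |
|---|---|---|---|
| Elective procedure planned before consent | Hospitalization criterion does not apply | Not an SAE | No |
| Social or convenience admission | Hospitalization criterion does not apply | Not an SAE | No |
| Elective, arranged after consent, for a condition that began or worsened on study, no other SAE criterion met | SAE, by the hospitalization criterion | Not an SAE | Yes |

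Observation stays and emergency or urgent-care visits are not inpatient admissions under 13.7.2.1, so they create no conflict.

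**Is the third case inside the reporting period?** Yes. The window in 13.7.2.4 opens at informed consent and closes 30 days after the last dose, so an admission arranged and carried out on study can fall within it.

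**Does the safeguard in 13.7.2.1 cover it?** No. It deals with complications and prolonged stays, not with the condition that led to the admission.

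**Does the AE rule in 13.7.1.3 cover it?** In part. The condition is recorded as an AE, so the event is not lost. Its seriousness remains unsettled.

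**Does anything else reconcile the two?** No. Protocol 13.7.2.3 to 13.7.2.6 do not address it, nor do the amendment entries available, nor SAP 5.5.1 or 5.5.2.

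**Which outputs are exposed?** The 24-hour report is exposed for any such event after consent. The tables in SAP 5.5.1 are exposed only if the event is also treatment-emergent, that is, if it began or worsened after the first dose of IMP (protocol 13.7.1.7).

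**Size of one event.** The change in an arm's SAE incidence is 1/n, where n is the number of subjects in the arm.

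- Protocol 14.2, n = 56: 1/56 = 0.0179, or 1.8 percentage points.
- SAP 4.4, n = 78: 1/78 = 0.0128, or 1.3 percentage points.

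These are the effects of a single reclassified event. They do not estimate how many there would be.

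**The case against.** The strongest reply is that the bullet in 13.7.2.2 is only a short restatement of the note before it. It pairs preplanned and elective admissions with social and convenience ones, as the note does. The criterion itself speaks of an AE that requires hospitalization, which a careful investigator might not apply to a convenience admission. On that reading most sites would classify alike. This lowers the likelihood of divergent classification but does not cure the text. The neighbouring overdose bullet carries an express exception for events that meet SAE criteria, and the hospitalization bullet carries none. A literal reader may fairly take it as unconditional.

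A second reply limits the scope, and it stands. The condition behind the admission is still an AE, complications and prolonged stays are still assessed for seriousness, and the remaining criteria in 13.7.2.1 (death, threat to life, disability, congenital anomaly, important medical event) are untouched. A reader might infer that treatment-emergent hospitalizations in general drop out of the SAE tables. The documents do not support that.

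A reader might also see a further contradiction in 13.7.2.5, which names coronary and noncoronary arterial revascularization and says "Serious AEs that are anticipated to occur in this subject population will be collected and reported by the investigator". That section concerns events already classed as serious and lists those exempt from expedited regulatory reporting. It does not make every revascularization an SAE, and if anything it steers an investigator towards collecting one as serious.

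Nor can the stakes be raised by saying that subjects go about 17 weeks without lipid-lowering treatment. Protocol 9.1 gives two of the three arms lipid-lowering study drug for 84 days, so only the placebo arm goes without for that long.

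**Conclusion.** The inconsistency is real and follows from the text alone. It is confined to an elective inpatient admission arranged after consent, for a condition that began or worsened on study and meets no other SAE criterion. For that case, 13.7.2.2 read literally removes SAE status, the 24-hour report and, where the event is treatment-emergent, its place in the serious-event tables.

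The size is 1.8 or 1.3 percentage points of an arm's SAE incidence per event, depending on whether 56 or 78 subjects per arm applies. The frequency cannot be obtained from the documents and is likely low over 12 weeks of treatment plus 30 days. It would be tempting to express one event as a share of an arm's expected SAEs. That needs an SAE rate the documents do not give, and the share would look large for any misclassified event when counts are small.

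A reader might also infer bias between arms. Under protocol 9.4 the sponsor, sites, CRO and subjects are blinded, so nothing in the documents suggests that misclassification would favour one arm. The issue is complete and consistent safety reporting. It should be corrected because the contradiction is certain and the repair small.

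**What to change.** Rewrite the first bullet of protocol 13.7.2.2 to carry the condition in 13.7.2.1. Hospitalization would be exempt only if it was for an elective or outpatient procedure already arranged when consent was signed, or if it was purely social or for convenience. Delete the free-standing reference to elective admissions.

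This uses the protocol's own rule and adds no new one. A further condition that the underlying illness has not worsened since consent would go beyond 13.7.2.1. It would be a separate decision for the sponsor and is not needed to remove the conflict.

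The cost is one bullet in a protocol amendment and possibly a few more SAE forms. The SAP needs no change on this point, because it takes the SAE classification as recorded.

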13.7.2.3. Clinical Laboratory Assessments as Adverse Events and Serious Adverse Events

It is the responsibility of the investigator to assess the clinical significance of all abnormal values as defined by the list of reference ranges from the local laboratory. In some cases, significant changes in lab values within the normal range will require similar judgment. Laboratory abnormalities should be reported as an AE if they meet any of the following criteria:

- Intervention is required to treat the abnormality.
- Modification of study treatment is required due to the abnormality.
- Based on the investigator's medical judgement.

13.7.2.4. Reporting Serious Adverse Events

All SAEs, regardless of relationship to IMP, occurring from the time of informed consent until 30 days following the last dose of IMP (for most subjects 30 days after Visit T3, must be reported by the principal investigator or designee to the authorized safety designee within 24 hours of the principal investigator or the clinical site becoming aware of the occurrence. All SAEs that the investigator considers related to IMP that occur after the 30-day follow-up of the study period must be reported to the sponsor.

To report the SAE, complete the provided SAE form and submit it to the safety designee within 24 hours of becoming aware of the occurrence.

The investigator is required to submit SAE reports to the IRB in accordance with local requirements. All investigators involved in studies using the same investigational product will

receive any safety alert notifications for onward submission to their local IRB as required. All reports sent to investigators will be blinded.

All SAEs should be recorded on the eCRF and source documents. Criteria for documenting the relationship to IMP and severity will be the same as those previously described.

The investigator must continue to follow the subject until the SAE has subsided or until the condition becomes chronic in nature, stabilizes (in the case of persistent impairment), or the subject dies.

Within 24 hours of receipt of follow-up information, the investigator must update the SAE form and submit any supporting documentation (eg, subject discharge summary or autopsy reports) to the safety designee.

13.7.2.5. Reporting of Serious Adverse Events to Regulatory Authorities

The sponsor (and/or designee) is responsible for submitting expedited reports of suspected and unexpected serious adverse reactions (SUSARS) to the appropriate regulatory authorities. All investigators participating in ongoing clinical studies with the IMP will be notified by the sponsor (or designee) of SUSARs. SUSARS must be communicated as soon as possible to the appropriate IRB by the investigator, as applicable and/or reported in accordance with local laws and regulations. Investigators should provide written documentation of IRB notification for each report to the sponsor.

Serious AEs that are anticipated to occur in this subject population will be collected and reported by the investigator as described in [Section 13.7.2.4](#). However, these events will not be submitted to the regulatory authorities as expedited reports unless they meet SUSAR criteria. The events that are considered exempt from expedited reporting include the following clinical endpoints:

- cardiovascular death;
- nonfatal myocardial infarction;
- nonfatal stroke;
- unstable angina requiring hospitalization;
- coronary revascularization;
- heart failure requiring hospitalization; and
- noncoronary arterial revascularization.

13.7.2.6. Reporting of Subject Death

The death of any subject during the study or within the 30-day follow-up period after they have completed the study (regardless of the cause) must be reported as detailed above.

13.7.2.7. Reports of Pregnancy

Although not considered an SAE (unless the event occurs with a serious outcome), pregnancy information on female subjects will be collected by the authorized safety designee. If a female

[figure not shown]
subject becomes pregnant during the study, study treatment should be discontinued immediately. The principal investigator or designee must complete and submit the Pregnancy Report Form within 24 hours of awareness of the pregnancy. In addition, subjects who become pregnant will complete the EOS evaluations according to the schedule in [Appendix 1](#). Whenever possible, pregnancies should be followed until outcome and the Pregnancy Outcome Reporting Form submitted to the safety designee once the outcome is known.

[figure not shown]
13.7.3. Adverse Events of Special Interest

[figure not shown]

The protocol procedures that are included in clinical studies of BA are part of standard clinical care for subjects with elevated LDL-C levels and, in addition, address the potential and theoretic risks of BA.

All BA studies will include standard pharmacovigilance including evaluation of AEs, PE findings, vital signs, and laboratory assessments. 

14. STATISTICS

14.1. General Considerations

The analyses described in this section will be performed as further outlined in the Statistical Analysis Plan, which will be finalized before the end of the study. The analyses specified in the Statistical Analysis Plan will supersede those specified in the protocol in the event of any differences between the two documents. A copy of the Statistical Analysis Plan will be included as an appendix in the clinical study report for this protocol.

14.2. Determination of Sample Size

The sample size of approximately 56 subjects per treatment arm (1:1:1) in this study (168 subjects total) is selected to provide adequate power for each of the co-primary endpoint as well as the co-primary endpoint family as a whole.

14.3. Analysis Populations

The following analysis populations will be defined:

- The full analysis set (FAS) will be used for the pharmacodynamic analyses and will include all randomized subjects who receive at least 1 dose of study drug and have a baseline and at least 1 measurable postbaseline lipid value, and having taken their study drug within 2 days of the lipid measurement. Subjects in the FAS will be included in their randomized treatment group, regardless of the treatment they actually received.
- Treatment Completer analysis set is a subset of full analysis set and will include subjects who complete 12-week treatment as indicated on the end of treatment CRF and have non-missing LDL-C value at Week 12
- The safety population (SP) will include all subjects who receive at least 1 dose of IMP. Subjects in the SP will be included in the treatment group that they actually received, regardless of their randomized treatment.

